## **8.0 COMPLIANCE TO CIP**

### **8.1 STATEMENTS OF COMPLIANCE**

The study will be performed in accordance with the most current versions of the FDA regulations, and any regional and/or national regulations, as appropriate.

The investigator will not start enrolling subjects or requesting informed consent from any subject prior to obtaining FDA and IRB approval.

## 8.2 ADHERENCE TO THE CLINICAL INVESTIGATION PLAN

A deviation is defined as an event where the clinical investigator, site personnel, sponsor or sponsor representative did not conduct the clinical study according to the Clinical Investigational Plan, IRB requirements or the Investigator Agreement. The investigator is not allowed to deviate from the CIP, except as specified under emergency circumstances.

In some cases, failure to comply with the CIP may be considered failure to protect the rights, safety and well being of subjects, since the non-compliance exposes subjects to unreasonable risks. For example, failure to adhere to the inclusion/exclusion criteria: these criteria are specifically defined by the investigator/manufacturer to exclude subjects for whom the drug is not beneficial and the use involves unreasonable risks. This may be considered failure to protect the rights, safety and well being of the enrolled subject. Similarly, failure to perform safety assessments intended to detect adverse events may be considered failure to protect the rights, safety and well being of the enrolled subject. Investigators should seek minimization of such risks by adhering to the CIP.

Simultaneously, in the event that adhering to the CIP might expose the subject to unreasonable risks, the investigator is also required to protect the rights, safety and well being of the subject by intentionally deviating from the requirements of the CIP, so that subjects are not exposed to unreasonable risks.

It is the responsibility of the investigator to provide adequate medical care to a subject enrolled in a study.

Regulations require that the PI maintain accurate, complete, and current records, including documents showing the date of and reason for every deviation from the Clinical Investigational Plan. Relevant information for each deviation will be documented on a Deviation Case Report Form.

Regulations require Investigators obtain approval from IRB before initiating changes in or deviations from the protocol, except when necessary to protect the life or physical well being of a subject in an emergency. Under emergency circumstances, deviations from the CIP to protect the rights, safety and well being of human subjects may proceed without prior approval of the IRB. Such deviations shall be documented and reported to the IRB as soon as possible, but no later than 5 working days.

## 9.0 ADVERSE EVENT, ADVERSE DRUG EFFECT, DRUG DEFICIENCY

### 9.1 DEFINITIONS

#### 9.1.1 Investigational drug

Any chemical

- Intended by the manufacturer to be used, alone or in combination, for human beings for one or more of the specific purpose(s) of
  - Diagnosis, prevention, monitoring, treatments or alleviation of disease,
  - Diagnosis, monitoring, treatment, alleviation of, or compensation for, an injury,
  - Investigation, replacement, modification, or support of the anatomy or of a physiological process,
  - Supporting or sustaining life,
  - Control of conception,
  - Disinfection of medical drugs and
- Which does not achieve its primary intended action in or on the human body by pharmacological, immunological or metabolic means, but which may be assisted in its intended function by such means

### 9.1.2 Adverse Event (AE)

- **Adverse Drug Reaction (ADR):** All noxious and unintended responses to a medicinal product related to any dose should be considered an adverse drug reaction. There must be evidence to suggest a causal relationship between the medicinal product and the adverse event, i.e. the relationship cannot be ruled out.
- **Adverse Event (AE):** Any unfavorable and unintended sign (including laboratory findings), symptom or disease that occurs to a subject while enrolled in a clinical investigation. Medical conditions that exist at study enrollment are not considered an AE unless condition worsens after enrollment.
  - **Serious Adverse Event (SAE) or Serious Adverse Drug Reaction (SADR):** Any untoward medical occurrence that at any dose:

1. Results in death
2. Is life threatening
3. Requires inpatient hospitalization or prolongation of current hospitalization related to the use of the study materials
4. Results in persistent or significant disability/incapacity
5. Results in a congenital abnormality or birth defect
6. Requires a medical or surgical intervention to prevent a permanent impairment of a body function or permanent damage to a body structure.

- **Unanticipated Adverse Event (UAE) / Unexpected Adverse Drug Reaction (UADR)/or Other Unexpected Problems:** Unexpected (in terms of nature, severity, or frequency) means that:

1. The event and/or reaction was not previously described in the research procedures included in the protocol-related documents, such as the protocol, or consent document, or in other relevant sources of information, such as product labeling or package inserts.

OR

2. The event and/or reaction was not previously described given the characteristics of the participant or the participant population being studied such as natural progression of any underlying disease, disorder or condition of the participant experiencing the adverse event/reaction, and the participants predisposing risk factor profile for the adverse event/reaction.

- **Relatedness to study drug or participation in the research.** The investigator will determine the causality of the AE or SAE (definitely not related, probably not related (unlikely), possibly related, probably related, definitely related).
- **Problem** suggests that the research places subject or others at a greater risk of harm (physical, psychological, economic, or social harm) than was previously known or recognized.
- **Unanticipated / unexpected problems involving risks to participants or others** are defined as meeting all of three of the following criteria:
  1. The event is unanticipated because it is not included in the currently approved research study documents, package insert, or study protocol or the event exceeds the described frequency or severity, or it is unexpected that it would occur given the study population described in the research. AND
  2. The event is definitely related, probably related or possibly related to procedures involved in the research. AND
  3. The event suggests that the research places the participants or others at a greater risk of harm than previously thought.

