#### **4.3.2 Secondary Objective**

Demonstrate safety and effectiveness of the amiodarone hydrogel application during lung transplantation in preventing atrial arrhythmias during first year of transplantation.

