### Assessment of Clinical Adverse Events

The subject's medical record will be accessed to determine the occurrence of any adverse events. The study team will review the medical records in a timely manner to determine adverse events and enable timely reporting:

1. Type of event
2. Date of onset and resolution (duration)
3. Severity (mild, moderate, severe)
4. Seriousness (does the event meet the above definition for an SAE)
5. Causality, relation to investigational product and disease
6. Action taken regarding investigational product
7. Outcome

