## 9.3 PROCEDURE FOR ASSESSING, RECORDING, AND REPORTING ADVERSE EVENTS, DRUG DEFICIENCIES/COMPLAINTS, ADVERSE DRUG EFFECTS, SERIOUS ADVERSE EVENTS, AND SERIOUS ADVERSE DRUG EFFECTS:

Safety surveillance within this study and the safety reporting both performed by the investigator, starts after the subject is enrolled in this study (date of signature of the informed consent) and has undergone the study intervention. The safety surveillance and the safety reporting will continue until the last investigational visit has

been performed, the subject is deceased, the subject/investigator concludes his/her participation in the study, or the subject/investigator withdraws the subject from the study.

All adverse event data including deaths will be collected throughout the clinical study and will be recorded on a dedicated case report form.

Records relating to the subject's subsequent medical course will be maintained at the site until the overall outcome has been ascertained and the record retention period for the site has expired. Adverse events related to the study intervention will be monitored until they are adequately resolved. The status of the subject's condition will be documented at each visit.

It is the responsibility of the Investigator or Sub-Investigator(s) to perform periodic assessments of all AEs as well as identifying SAEs. The AE and SAE reporting period for this study is from the study intervention through study termination. Any AEs, ADEs, SAEs and SADEs that occur during the study will be treated by established standards of care that will protect the life and safety of the subjects.

If at the time the Investigator completes an initial SAE form and the SAE has not resolved, the Investigator will complete a follow-up report as soon as the event resolves (or upon receipt of significant information if the event is still ongoing).

All AEs and ADRs will be reported in the subjects' research record. Any serious, related, and unanticipated adverse events will be reported to the IRB within 5 working days of awareness of the event. All drug related, serious, unanticipated adverse drug reactions will be reported to the company and FDA within 15 working days of the event.

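### SAE criterion 3 in section 9.1.2 makes hospitalization or prolonged stay serious only if attributed to the study materials, so one of six seriousness criteria depends on the causality judgement

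*Combined protocol and SAP*

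**What the plan says.** Section 9.1.2 uses one list of six criteria to define both a serious adverse event and a serious adverse drug reaction. The lead-in sets no causal condition: "Any untoward medical occurrence that at any dose". Criterion 3 does: "Requires inpatient hospitalization or prolongation of current hospitalization related to the use of the study materials". The other five (death, threat to life, disability, congenital abnormality, and the last, "Requires a medical or surgical intervention to prevent a permanent impairment of a body function or permanent damage to a body structure") have no such condition.

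The same section then treats causality as a separate grading that applies to serious events too: "The investigator will determine the causality of the AE or SAE (definitely not related" is the first of five grades.

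In section 9.2, under the assessment of clinical adverse events, item 4 is "Seriousness (does the event meet the above definition for an SAE", which points back to the six criteria. Item 5 is "Causality, relation to investigational product and disease".

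Section 9.3 provides that "All AEs and ADRs will be reported in the subjects' research record". It requires a follow-up report when an SAE has not resolved by the time the initial SAE form is completed. It limits expedited reports to the IRB, the company and FDA to events that are serious, unanticipated and related. Section 7.0 repeats that rule.

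**The concern.** Seriousness describes the outcome or the care an event required. Causality is an opinion about its origin. Criterion 3 needs the second before it can settle the first, so the site cannot answer item 4 on this criterion until it has answered item 5.

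This matters because safety is an objective both for the index stay (section 4.3.1) and for the first year (section 4.3.2: "Demonstrate safety and effectiveness of the amiodarone hydrogel application during lung transplantation"). Every subject is an inpatient when the gel is applied. Section 3.3.2 lists many transplant complications to which a later event can be attributed, whereas sections 3.3.1 and 7.0 single out temporary bradycardia as the risk added by the study. The investigator makes the attribution knowing that every prospective subject received the gel. On criterion 3, an SAE tally would therefore hold only events already attributed to the product, and a pattern among events judged unrelated one by one would not show in it.

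**Working it through.** No sample size, power or event count in the plan bears on this point, so there is no stated figure to reproduce. The check compares the texts and then tests how far any statement about size can go.

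**Step 1: how an unrelated event is classified.** Take an adverse event that leads to readmission or a longer stay and is graded unrelated.

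| Rule | Result |
|---|---|
| 9.1.2, lead-in | No causal condition; the event is eligible |
| 9.1.2, criteria 1, 2, 4, 5, 6 | Serious if any one is met, whatever the cause |
| 9.1.2, criterion 3 | Not serious, because it is unrelated |
| 9.1.2, causality grading | Expects that SAEs graded definitely unrelated can exist |
| 9.2, items 4 and 5 | Two separate judgements |
| 9.3, AE record | Recorded in either case |
| 9.3, SAE follow-up report | Not triggered unless another criterion is met |
| 7.0 and 9.3, expedited reports | Not reportable in either case, because it is unrelated |

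The third row conflicts with the fourth and fifth. The practical effect is confined to SAE classification and to the SAE follow-up report.

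**Step 2: the two readings of criterion 3.** The condition may govern both hospitalization and prolongation, or only prolongation. On the first reading, readmissions and prolonged stays are both affected. On the second, every readmission due to an adverse event is serious and only unrelated prolongations are affected. The conflict in step 1 exists on either reading.

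**Step 3: size.** Let r be the share of affected-type events judged related, and q the share of the unrelated ones that meet another criterion. The share recorded as non-serious is (1 − r)(1 − q). The documents give neither r nor q. The values below are assumptions, over r = 0 to 0.30 and q = 0 to 0.60.

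- r = 0, q = 0: 1.00 × 1.00 = 100%
- r = 0.05, q = 0.10: 0.95 × 0.90 = 85.5%
- r = 0.10, q = 0.30: 0.90 × 0.70 = 63%
- r = 0.10, q = 0.50: 0.90 × 0.50 = 45%
- r = 0.30, q = 0.60: 0.70 × 0.40 = 28%

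The share exceeds one half only if q < 1 − 0.5/(1 − r). That limit is 0.474 at r = 0.05, 0.444 at r = 0.10, 0.375 at r = 0.20 and 0.286 at r = 0.30. Whether more or fewer than half of such events are affected therefore depends on two unknown shares.

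**Step 4: after the change.** Without the condition, every adverse event requiring hospitalization or prolongation meets criterion 3, and the share becomes 0 for any r and q. No sample size or power figure changes.

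**The case against.** The strongest reply is that little is lost. Five of the six criteria are free of the condition, and a serious complication after transplant will often meet one of them; a readmission for respiratory failure, for example, may count as life-threatening. All AEs are recorded, and section 9.2 asks for severity, causality, dates of onset and resolution, and outcome for each. Length of the initial stay is a secondary endpoint (synopsis and section 4.4.2) and is compared between groups without any causality judgement, so an excess of prolonged index stays stays visible. Deaths are serious whatever their cause. All of this stands, and it limits the consequence. It does not explain the condition or remove the conflict, and readmission has no endpoint of its own.

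One might also guess that the phrase keeps the planned transplant admission out of the SAE count. The lead-in, which is limited to untoward occurrences, already does that.

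A reader might infer more than the text supports, in four ways:

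- *That most hospitalizations vanish from the SAE record.* Step 3 shows that this depends on two shares the documents do not give.
- *That safety reports to the IRB or FDA are lost.* Expedited reporting already requires relatedness, so no such report turns on criterion 3.
- *That the final report would understate an SAE rate.* Section 17.3 requires a final report, but no SAE rate, listing or comparison with controls is defined anywhere in the plan.
- *That bradycardia prolonging the stay would be classed as non-serious once surgery is blamed.* In section 9.2, the possibly-related grade covers a known response pattern with reasonable timing even when the clinical state is a rival cause, and bradycardia is the anticipated effect of the gel.

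**Conclusion.** The point holds in a limited form. One of six seriousness criteria depends on attribution, contrary to the protocol's own separation of seriousness from causality. Hospitalizations or prolongations judged unrelated that meet no other criterion become non-serious AEs, outside any SAE tally and without the SAE follow-up report. On the narrower reading, this applies to prolongations only. The events are not lost from the AE record. The number affected cannot be derived from the documents, and the percentages in step 3 are illustrations over assumed ranges. The conclusion rests on the site applying criterion 3 as written.

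**What to change.** In criterion 3 of section 9.1.2, delete the closing phrase that ties the event to the study materials, so that the criterion ends after the words on prolonging the current hospitalization. This also removes the ambiguity about what the phrase modifies. Leave relatedness to item 5 of the section 9.2 assessment. The serious adverse drug reaction category keeps its causal element, because the definition of an adverse drug reaction in section 9.1.2 already supplies it.

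The cost is more SAE forms and follow-up reports, since unrelated hospitalizations and prolongations would then count as serious. Expedited reporting of unrelated events does not grow, because sections 7.0 and 9.3 still require relatedness. Sample size, endpoints and treatment are untouched.

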## 9.2 REPORTING OF ADVERSE EVENTS/REACTIONS

Adverse events are generally detected in two ways:

**Clinical:** Symptoms reported by the subject or signs detected on examination.

**Ancillary testing:** abnormalities of vital signs, laboratory tests, and other diagnostic procedures (other than outcome measures: the results of which are not being captured as AEs).

### Assessment of Clinical Adverse Events

The subject's medical record will be accessed to determine the occurrence of any adverse events. The study team will review the medical records in a timely manner to determine adverse events and enable timely reporting:

1. Type of event
2. Date of onset and resolution (duration)
3. Severity (mild, moderate, severe)
4. Seriousness (does the event meet the above definition for an SAE)
5. Causality, relation to investigational product and disease
6. Action taken regarding investigational product
7. Outcome

### Relatedness of Adverse Event to Investigational Product

The relationship of the AE to the investigational product should be specified by the Site, using the following definitions:

1. **Definitely Not Related:** Concomitant illness, accident or event with no reasonable association with treatment.
2. **Unlikely (probably not related):** The reaction has little or no temporal sequence from administration of the investigational product, and/or a more likely alternative etiology exists.
3. **Possibly Related:** The reaction follows a reasonably temporal sequence from administration of the investigational product and follows a known response pattern to the suspected investigational product; the reaction could have been produced by the investigational product or could have been produced by the subject's clinical state or by other modes of therapy administered to the subject. (suspected ADR)
4. **Probably Related:** The reaction follows a reasonably temporal sequence from administration of investigational product; is confirmed by discontinuation of the investigational product or by re-challenge; and cannot be reasonably explained by the known characteristics of the subject's clinical state. (suspected ADR)
5. **Definitely Related:** The reaction follows a reasonable temporal sequence from administration of investigational product; that follows a known or expected response pattern to the investigational product; and that is confirmed by improvement on stopping or reducing the dosage of the investigational product, and reappearance of the reaction on repeated exposure. (suspected ADR)

## 9.3 PROCEDURE FOR ASSESSING, RECORDING, AND REPORTING ADVERSE EVENTS, DRUG DEFICIENCIES/COMPLAINTS, ADVERSE DRUG EFFECTS, SERIOUS ADVERSE EVENTS, AND SERIOUS ADVERSE DRUG EFFECTS:

Safety surveillance within this study and the safety reporting both performed by the investigator, starts after the subject is enrolled in this study (date of signature of the informed consent) and has undergone the study intervention. The safety surveillance and the safety reporting will continue until the last investigational visit has

been performed, the subject is deceased, the subject/investigator concludes his/her participation in the study, or the subject/investigator withdraws the subject from the study.

All adverse event data including deaths will be collected throughout the clinical study and will be recorded on a dedicated case report form.

Records relating to the subject's subsequent medical course will be maintained at the site until the overall outcome has been ascertained and the record retention period for the site has expired. Adverse events related to the study intervention will be monitored until they are adequately resolved. The status of the subject's condition will be documented at each visit.

It is the responsibility of the Investigator or Sub-Investigator(s) to perform periodic assessments of all AEs as well as identifying SAEs. The AE and SAE reporting period for this study is from the study intervention through study termination. Any AEs, ADEs, SAEs and SADEs that occur during the study will be treated by established standards of care that will protect the life and safety of the subjects.

If at the time the Investigator completes an initial SAE form and the SAE has not resolved, the Investigator will complete a follow-up report as soon as the event resolves (or upon receipt of significant information if the event is still ongoing).

All AEs and ADRs will be reported in the subjects' research record. Any serious, related, and unanticipated adverse events will be reported to the IRB within 5 working days of awareness of the event. All drug related, serious, unanticipated adverse drug reactions will be reported to the company and FDA within 15 working days of the event.

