	
4) Subjects willing and able to comply with the follow up requirements of the study
 
Exclusion Criteria
 
 
1) Patients with previous history of atrial fibrillation.
 
2) Patients with previously documented allergy or adverse reaction to amiodarone.
 
3) Patients with previous ablation for atrial fibrillation
 
4) Patients with an implantable pacemaker.
 
 
•

Data Collection
	
Subjects will be evaluated and enrolled for receiving the amiodarone gel during their waiting period for lung transplantation.
 
Patients who consent to be part of the study will receive the amiodarone gel during the surgery for lung transplantation. The amiodarone gel will be sprayed just after transplanting the lung(s). Patients will then be followed in-hospital until discharge and data regarding the primary study end-point will be captured.
 
Patient study visit follow-up will occur post-operatively as per standard of care after lung transplantation. Patients' follow-up is generally comprised of routine history and physical examination. These will provide sufficient data to address the secondary study end-points. All follow up data will be collected from the subject's medical records.
 
•

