### **6.3 EARLY TERMINATION**

The study team will attempt to collect all relevant information for the study subjects who withdraw from the study early (including CRF Study Completion Form). The following information will be collected:

- Updated medical and surgical history
- Assessment of AEs that occurred since the last visit
- Abbreviated physical examination (only significant changes since Enrollment) including vital signs (temperature, heart rate, respiratory rate, blood pressure), and weight
- Medication Review

All reasonable efforts will be made to retain subjects in the clinical trial until its completion. Subjects lost to follow-up will be withdrawn only after a minimum of two documented phone calls are made by personnel at the study center to the patient or emergency contact.

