### **6.4 CRITERIA AND PROCEDURES FOR SUBJECT WITHDRAWAL OR DISCONTINUATION**

Subjects must be informed about their right to withdraw from the study at any time and for any reason without sanction, penalty or loss of benefits to which the subject is otherwise entitled and withdrawal from the study will not jeopardize their future medical care or relationship with the investigator. Subjects will be asked to specify the reason for the termination, but have the right not to answer.

The investigator may decide to withdraw a subject from the study at any time with reasonable rationale. The subject's future care will not be influenced by a decision, voluntary or otherwise, to withdraw from the study. All reasonable efforts should be made to retain the subject in the clinical study until completion of the study.

Reasons for subject's withdrawal include, but are not limited to:

- Subject refuses to continue participating in the study
- Subject does not meet the inclusion/exclusion criteria and does not require additional follow-up for safety reasons.
- Subject is deceased (cause must be documented)
- Subject's non-compliance
- Subject's participation is terminated by the PI or investigator, although the subject consented, since participation is no longer medically appropriate
- Subject is 'lost to follow up': Subject does not adhere to the scheduled follow up visits but has not explicitly requested to be withdrawn from the clinical study. Site personnel should at all times make

all reasonable efforts to locate and communicate with the subject in order to achieve subject compliance to the scheduled follow up visits:

1. A subject will be considered 'Lost to Follow Up' after a minimum of 2 phone calls of a physician or delegate at the investigational site to the subject or contact. These 2 phone calls need to be documented in the subject's hospital records.

Note: If a subject misses one or more of the scheduled follow up visits (inclusive of the assigned visit windows), this will be considered as a missed visit. The subject may therefore still return for subsequent visits and will not be excluded from the study.

If a subject withdraws from the clinical study, the site will record the subject's reasons for withdrawal (if available), on a Withdrawal CRF.

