When subject withdrawal from the clinical study is due to a study related adverse event the subject will be followed until resolution of that adverse event or determination that the subject's condition is stable. The status of the subject's condition should be documented at the time of withdrawal.

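### Sections 6.3, 6.4, 9.3 and 10 conflict on whether safety and survival data are still collected after an investigator withdraws a patient who has not withdrawn consent

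*Combined protocol and SAP*

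**What the plan says.** **The stop.** Section 9.3 lets surveillance and reporting run until the last study visit, death, the end of participation, "or the subject/investigator withdraws the subject from the study".

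**Routes to withdrawal.** Section 6.4 states: "The investigator may decide to withdraw a subject from the study at any time with reasonable rationale". Its list of reasons includes "Subject's non-compliance", a judgement that continuing is medically unsuitable, and loss to follow-up. It describes the last group as patients who have not asked to leave. Section 6.3 adds: "Subjects lost to follow-up will be withdrawn only after a minimum of two documented phone calls". Of a patient who only misses visits, 6.4 says: "The subject may therefore still return for subsequent visits and will not be excluded from the study".

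**Text pointing the other way.** Section 9.3 also sets the reporting period for AEs and serious AEs from the intervention to study termination. Sections 9.3 and 10.1.1 have all deaths collected for the duration of the study.

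**Exceptions.** Section 6.4 provides: "When subject withdrawal from the clinical study is due to a study related adverse event the subject will be followed" to resolution or stability. Section 9.3 has AEs related to the intervention monitored until resolved. Section 6.3 seeks a final history, AE review, short examination and medication review at early withdrawal.

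**Design.** Section 3.4 describes a single application. The Synopsis says: "All follow up data will be collected from the subject's medical records". Section 4.3.2 makes first-year safety and effectiveness the secondary objective. Section 4.4.2 lists first-year AF and one-year survival as endpoints.

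**The concern.** In a trial of continuing treatment, withdrawal at least stops exposure. Here the gel is already in place when any post-operative withdrawal occurs, so withdrawing a patient who has not withdrawn consent mainly stops data collection. The data in question come largely from standard-of-care records, which continue to exist.

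First-year safety, first-year AF and one-year survival are at stake. Patients who stop attending, or whom the investigator judges unsuitable to continue, may differ in prognosis from those who remain. If they are sicker, the gel group's one-year results would look better than they are. The comparison is also uneven. Section 4.2 draws the controls retrospectively from records and database entries, so these withdrawal rules act only on the gel group. The primary endpoint, AF during the initial hospitalization, is largely unaffected.

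**Working it through.** **1. The texts side by side.** No figure in the plan bears on this point, so there is nothing to reproduce. The question is what happens to a patient whom the investigator withdraws after discharge for non-compliance or lost contact.

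| Item after withdrawal | Under the explicit stop in 9.3 | Under the other text |
|---|---|---|
| Related AE already under way | Monitored to resolution (9.3) | Same |
| Withdrawal caused by a study-related AE | Followed to resolution or stability (6.4) | Same |
| New AE, or one not judged related | Not sought | Reported to study termination (9.3) |
| Death | Not sought | Collected (9.3, 10.1.1) |
| First-year AF | No provision | No provision |

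If study termination means the end of the whole study, rows 3 and 4 are in direct conflict. If it means the end of that patient's participation, the conflict disappears but the stop governs. Either way, no section states that record review or a vital-status check continues to one year. The early-termination assessment in 6.3 looks back to the last visit, not forward.

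**2. What one loss is worth.** Section 4.2.3 plans at least 20 treated patients, so one patient is 1/20 = 5 percentage points.

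**3. Bounds on one-year mortality.** The plan gives no loss rate, so losses are assumed. With d observed deaths and k patients of unknown status among 20, mortality lies between d/20 and (d + k)/20. For d = 2:

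- k = 1: 2/20 to 3/20, or 10% to 15%.
- k = 2: 2/20 to 4/20, or 10% to 20%.
- k = 4: 2/20 to 6/20, or 10% to 30%.

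These bounds need no assumption about why patients were lost.

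**4. Harms not observed.** With no events in n patients, the one-sided 95% upper bound is 1 − 0.05^(1/n). The chance of seeing at least one case of a harm with true risk 10% is 1 − 0.9^n.

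- n = 20: bound 13.9%, chance 87.8%.
- n = 16 (4 lost, assumed): bound 17.1%, chance 81.5%.

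This treats a lost patient as contributing nothing, which slightly overstates the effect if part of the year was observed.

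**5. When bias arises.** Let q be true one-year mortality, and let Ld and Ls be the loss among those who die and those who survive. If lost patients leave the denominator, expected observed mortality is q(1 − Ld) / [q(1 − Ld) + (1 − q)(1 − Ls)]. Assume q = 15% and Ls = 10%:

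- Ld = 10%: 0.135/(0.135 + 0.765) = 15.0%, no bias.
- Ld = 30%: 0.105/(0.105 + 0.765) = 12.1%.
- Ld = 50%: 0.075/(0.075 + 0.765) = 8.9%.

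Loss unrelated to outcome costs precision only. Loss related to outcome biases the result.

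**The case against.** The strongest reply is that the protocol already intends complete collection. Section 9.3 reports AEs to study termination, deaths are recorded in all cases, and records of the later medical course are kept until the outcome is known. Section 4.5 says withdrawn and lost patients will be accounted for. Related AEs are followed, 6.3 asks for a final assessment, and 6.4 asks for all reasonable efforts to locate patients. This stands as evidence of intent. It does not cancel an explicit stopping rule in the same section, and the exceptions do not cover new events, unrelated events or AF.

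Four stronger readings are tempting but go beyond the documents:

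- A reader might infer that late harms and deaths will be lost, and lost selectively. The text is contradictory rather than clear on loss, and selectivity is plausible but not shown.
- A reader might infer that two unanswered calls end follow-up. Two documented calls are a minimum, the text does not say they go unanswered, and the duty of reasonable efforts sits beside them.
- A reader might see 6.4 as contradicting itself on missed visits. Missing a visit and becoming lost can be two successive states. What remains is an ambiguity, since no interval separates them.
- A reader might compute survival of 15/18 (83%) in place of 15/20 (75%) if two deaths followed withdrawal. That assumes withdrawn patients leave the one-year denominator. Section 14.1 excludes those who leave before the primary endpoint and those who withdraw consent, and is silent on patients the investigator withdraws later.

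Two limits on the remedy also stand. Site records may miss events treated elsewhere. The consent and authorization form is not in the text reviewed and may govern use of records after withdrawal.

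**Conclusion.** The point holds as an unreconciled conflict with a real consequence. Under the explicit stop, a compliant site can lose new AEs, AEs not already judged related, first-year AF and one-year vital status for patients who never withdrew consent. Nothing in a one-time application with record-based follow-up requires this.

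Each such patient is 5 percentage points of a 20-patient group. Two losses alongside 2 observed deaths leave mortality bounded only at 10% to 20%; the numbers lost and the deaths are assumptions. Any bias depends on loss being related to outcome, and its size also depends on a denominator rule the plan does not state. The effect falls on late safety and secondary endpoints of a pilot. The change is therefore worth making, but this point does not threaten the primary analysis.

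**What to change.** Reconcile 6.3, 6.4, 9.3 and 10 so that one rule governs the end of data collection:

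- After gel application, only death or withdrawal of consent ends data collection before one year.
- For non-compliance, investigator decision, later ineligibility or loss of contact, missed visit data are recorded as missing. Review of available records for AEs, AF and vital status continues to 12 months, as the consent and authorization allow.
- Section 14.1 states that these patients stay in the one-year analyses and says how unknown status is handled, for example by reporting the bounds shown above.

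The cost is protocol wording and a few extra chart reviews, with no added study visits. A vital-status check beyond the site's own records would be some further work. Events treated elsewhere may still be missed, so the report should give the number of patients with incomplete one-year information.
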